4.8.3 Screening and eligibility assessment (Screening visit)

All potential volunteers will have a screening visit, which may take place up to 30 days prior to enrolment. Once informed consent is given, a screening number will be assigned in sequential order. Screening numbers will be issued consecutively (e.g. RTS-SC-001, RTS-SC-002, RTS-SC-003,...). This will be recorded in the Case Screening Form, together with the demographic information and procedures performed to determine eligibility. Screening procedures indicated in the schedule of procedures (Appendix A) will be undertaken. If a screening haematology or biochemistry test result is deemed clinically significant it may be repeated to ensure it is not a single occurrence. If an abnormal finding at screening is deemed to be clinically significant, the volunteer will be informed and appropriate medical care arranged with the permission of the volunteer. In the unlikely event that a volunteer is found to have malaria or anaemia the volunteer will be treated according to national guidelines and will be excluded from participating in the study.

4.8.4 Enrolment, baseline assessment, regimen allocation, and first vaccination (Month 0 / Day 0 visit; Baseline visit)

All inclusion and exclusion criteria will be checked before enrolment in the study. Physical examination will be performed. Any new medical issues or symptoms that have arisen will be assessed. Blood will be collected for baseline parasite microscopy, haemoglobin and biochemistry. Participants with parasitaemia or anaemia will be treated according to national guidelines. Blood will be collected and stored for measurement of antibodies against *P. falciparum* circumsporozoite (anti-CS antibody) until shipment to the reference laboratory. Urine will be collected from women of child-bearing age for immediate pregnancy test.

If interval between screening and enrolment is three days or less, the screening test results (parasite microscopy, haemoglobin, biochemistry, and urine pregnancy test) can be used for

enrolment evaluation. In such cases, these tests (parasite microscopy, haemoglobin, biochemistry, and urine pregnancy test) would not need to be repeated at the baseline (Month 0 / Day 0) visit. If all inclusion criteria are fulfilled and none of the exclusion criteria apply, the patient will be enrolled into the study and a CRF specific to each participant completed. Regimen allocation and administration of the vaccine(s) will be on Day 0. The randomization lists will be prepared by MORU.

Randomization numbers will be generated in blocks, for the 7 intervention arms in a ratio of 20:20:30:30:30:30:30, as follows:

- RTS,S/AS01B Fractional dose group (Group 1)
- Double RTS,S /AS01E Fractional dose group (Group 2)
- RTS,S/AS01E Standard dose group (Group 3)
- RTS,S/AS01E + DHA-PIP+PQ Standard dose group (Group 4)
- RTS,S/AS01E Fractional dose group (Group 5)
- RTS,S/AS01E + DHA-PIP+PQ Fractional dose group (Group 6)
- RTS,S/AS01E + DHA-PIP+PQ Fractional two-dose group (Group 7)

Study participants will be assigned the next available randomization number on the list, and thus will be randomly allocated to Group 1, 2, 3, 4, 5, 6 or 7. This is an open-label study and participants and clinical investigators will not be blinded to group allocation.

Subjects will then be vaccinated by intramuscular (IM) needle injection into the deltoid region of the arm. Subjects in Groups 4, 6 and 7 will also receive anti-malarial medications.

The study participants will be observed closely for at least 30 minutes following the administration of each study vaccine, with appropriate medical treatment readily available in case of an anaphylactic reaction.

An oral thermometer, tape measure and a paper diary card for solicited AEs will be given to each participant along with the emergency 24 hour telephone number to contact the on call study physician if needed. Diary cards will collect information on the timing and severity of the following solicited AEs:

Local solicited AEs	Systemic solicited AEs
Pain at injection site	Fever
Redness at injection site	Gastrointestinal symptoms (nausea, vomiting, diarrhoea and/or abdominal pain)
Swelling at injection site	Fatigue
	Headache

Participants will be instructed on how to self-assess the severity of these AEs. There will also be space on the diary card to self-document unsolicited AEs, and whether medication was taken to relieve the symptoms.

4.8.5 Subsequent vaccination visits (Month 1 / Day 0 and Month 2 / Day 0 visits)

Subsequent vaccination visits will be done according to the schedule of procedures (Appendix A). Physical examination will be performed. Any new medical issues or symptoms that have arisen will be assessed. Blood will be collected for parasite microscopy. Participants with parasitaemia or anaemia will be treated according to national guidelines. Blood will be collected and stored for measurement of antibodies against *P. falciparum* circumsporozoite (anti-CS antibody) until shipment to the reference laboratory. Urine will be collected from women of child-bearing age for immediate pregnancy test.

Before vaccination, the on-going eligibility of the volunteer will be reviewed. All participants will attend the clinic for vaccination visits, will be observed closely for at least 30 minutes following the administration of each study vaccine, and will receive a paper diary card for recording solicited AEs, as described above. Information will be recorded in the CRF for subsequent vaccination visits.

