4.3.3 Exclusion Criteria

The following criteria should be checked at the time of study entry. If ANY exclusion criterion applies, the subject must not be included in the study:

- Female participant who is pregnant, lactating or planning pregnancy during the course of the study.
- Presence of any condition which in the judgment of the investigator would place the participant at undue risk or interfere with the results of the study (e.g. serious underlying cardiac, renal, hepatic or neurological disease; severe malnutrition; congenital defects or febrile condition).
- Hepatitis B surface antigen (HBsAg) detected in serum.
- Screening ECG demonstrates a QTc interval ≥ 450 ms

- Seropositive for hepatitis C virus (antibodies to HCV) at screening (unless has taken part in a prior hepatitis C vaccine study with confirmed negative HCV antibodies prior to participation in that study, and negative HCV RNA PCR at screening for this study).
- Anaemia (Hb < 10 g/dL)
- Positive malaria parasitaemia at screening or baseline (Month 0, Day 0).
- Use of any investigational or non-registered product or investigational use of a registered product (drug or vaccine), other than the study vaccines, during the period from the date of screening to the first vaccination, or planned use during the study period.
- Any medical condition that in the judgment of the investigator would make intramuscular (IM) injection unsafe.
- Any medical condition that in the judgment of the investigator would make the administration of the antimalarial treatment unsafe, such as prior allergic reactions to one or more component of the drug regimen: artemisinin, piperazine or primaquine.
- Contraindications to the use of artemisinin, piperazine or primaquine or use of medications known to have a potentially clinically significant interaction with these medications.
- Chronic administration (defined as more than 14 days in total) of immunosuppressants or other immune-modifying drugs during the period starting six months prior to the first vaccine dose. For corticosteroids, this will mean prednisone > 20 mg/day (for adult subjects), or equivalent. Inhaled and topical steroids are allowed.
- Planned administration/administration of a vaccine not foreseen by the study protocol in the period starting seven days before the first dose.

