4.12 Pregnancy

Participants are informed that the safety of the vaccine in pregnancy is unknown. Female study participants are asked to use appropriate contraceptive methods to prevent pregnancy while they receive vaccinations. Appropriate contraceptive methods include:

- Established use of oral, injected or implanted hormonal contraceptives
- Intrauterine Device or Intrauterine System
- Barrier methods (condoms or diaphragm with additional spermicide)
- Male sterilisation (with appropriate post-vasectomy documentation of absence of sperm in the ejaculate)

- True abstinence, when this is in line with the preferred and usual lifestyle of the subject. Periodic abstinence (e.g., calendar, ovulation, symptothermal, post-ovulation methods) and withdrawal are not acceptable methods of contraception.

Female participants will be tested for pregnancy immediately prior to each vaccination.

Should a participant become pregnant during the trial, she will be followed up as other volunteers and in addition will be followed until pregnancy outcome, with the participant's permission. We will not routinely perform venepuncture on such participants.

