Ask about any concomitant medication	x	x	x ^b	x ^b	x	x	x ^b	x ^b	x	x	x ^b	x ^b	x	x	x	
Assessment of any adverse event(s)		x	x ^b	x ^b	x	x	x ^b	x ^b	x	x	x ^b	x ^b	x	x	x	
Assess for any withdrawal criteria		x	x ^b	x ^b	x	x	x ^b	x ^b	x	x	x ^b	x ^b	x	x	x	
Blood sample (mL)	Parasite microscopy****					0.5				0.5					0.5	
	Haematology Hb, WBC, PLT	2	2		2				2				2	2		
	Biochemistry ALT, AST, CREA	3	3		3				3				3	3		
	HBsAg, HCV, HIV	1														
	Immunology panel ^c		10			10				10				10	10	
	Piperazine & Primaquine levels*****		1 ^g	1 ^e	1 ^d	1 ^d	1 ^d	1 ^e	1 ^d	1 ^d	1 ^d	1 ^e	1 ^d			
	Blood volume per visit (mL)	6	16	1	1	6	11.5	1	1	6	11.5	1	1	6	15	10.5
	Maximum cumulative blood volume (mL)															94.5
Electrocardiogram (ECG)	x															
Urine pregnancy test	x	x				X				x						

* Procedures are not applicable for study group 7

** Only for study groups 4, 6 and 7, where applicable

*** Axillary temperature will be record from D0-D7 after each vaccination

a) first day of M6

b) Visits on days 1 and 2 post-vaccination are only applicable for study groups 4, 6, and 7 in Months 0 and 2, and for study groups 4 and 6 in Month 1.

c) the immunology panel consists of six assays to be processed at WRAIR:

**** Parasite microscopy for purposes of indicating whether volunteer has been exposed, and not as an assessment of protection.
 
***** Piperaquine and Primaquine levels for group 4 and 6 only. Additional drug level assessment for Primaquine will be done if additional data are required.
	
 • Plasmodium falciparum. Circumsporozoite Protein. (NANP)6 Ab.IgG • Plasmodium falciparum. Circumsporozoite Protein. (NANP)6 Ab.IgG Avidity • Plasmodium falciparum. anti-C-Term Circumsporozoite Ab.IgG • Plasmodium falciparum. anti-C-Term Circumsporozoite Ab.IgG avidity • Plasmodium falciparum. Circumsporozoite Full length (N+C-Terminal) • P falciparum. anti-full length CSP Ab.IgG avidity 
d) Drug level only for Piperaquine
 
e) Drug level for Piperaquine and Primaquine
 
f) If interval between screening and M0D0 is 3 days or less, screening lab results (haematology, biochemistry, parasite microscopy, and urine pregnancy test) can be used for enrolment (M0D0)
 
g) Drug level for Piperaquine and/or Primaquine will be assessed if additional data are required

---	---

Summary of participant visits

Group	Number of visit	Visit timepoints														

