		Scr	M0				M1				M2				M3	M6
			D0	D1	D2	D7	D0	D1	D2	D7	D0	D1	D2	D7	D0	D0
1	9	x	x			x	x			x	x			x	x	x
2	9	x	x			x	x			x	x			x	x	x
3	9	x	x			x	x			x	x			x	x	x
4	15	x	x	x	x	x	x	x	x	x	x	x	x	x	x	x
5	9	x	x			x	x			x	x			x	x	x
6	15	x	x	x	x	x	x	x	x	x	x	x	x	x	x	x
7	13	x	x	x	x	x	x			x	x	x	x	x	x	x

All the study procedure will be performed by research team including research doctor, research nurse and research physician at healthy volunteer unit at Faculty of Tropical Medicine, Mahidol University.

Intervals between study visits

Interval	Optimal length of interval	Allowed interval
Screening to Month 0 / Day 0 (1 st vaccination)	0 to 30 days	-
Month 0 / Day 0 (1 st vaccination) to Month 1 / Day 0 (2 nd vaccination)	28 days	+/- 7 days
Month 1 / Day 0 (2 nd vaccination) to Month 2 / Day 0 (3 rd vaccination)	28 days	+/- 7 days
Month 2 / Day 0 (3 rd vaccination) to Month 3 / Day 0	28 days	+/- 7 days
Month 3 / Day 0 to Month 6 / Day 0	84 days	+/- 14 days

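### The three-day carry-forward of the screening urine pregnancy test (Section 4.8.4, Appendix A footnote f) conflicts at dose 1 with Section 4.12, which requires a test immediately before every vaccination

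*Protocol*

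**What the plan says.** Three places in the current protocol set the timing of the pregnancy test before dose 1.

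- **Section 4.8.4** (enrolment and first vaccination) first calls for a urine test at the visit: "Urine will be collected from women of child-bearing age for immediate pregnancy test". It then qualifies this: "If interval between screening and enrolment is three days or less, the screening test results (parasite microscopy, haemoglobin, biochemistry, and urine pregnancy test") may be used for the enrolment evaluation. On repeat testing it adds: "In such cases, these tests (parasite microscopy, haemoglobin, biochemistry, and urine pregnancy test) would not need to be repeated at the baseline". The visit meant is the one on Day 0 of Month 0. The same section places allocation and the first vaccination on Day 0.
- **Appendix A, footnote f** repeats the waiver in the procedures schedule, again for an interval of up to three days: "screening lab results (haematology, biochemistry, parasite microscopy, and urine pregnancy test) can be used for enrolment (M0D0".
- **Section 4.12** (Pregnancy) states: "Female participants will be tested for pregnancy immediately prior to each vaccination". It names no exception and does not refer to Section 4.8.4.

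For Months 1 and 2, Section 4.8.5 requires an immediate urine test and contains no waiver.

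**The concern.** Where the waiver is used for the pregnancy test one to three days after screening, Sections 4.8.4 and 4.12 cannot both be followed. A monitor could record a deviation from 4.12, and the site could answer that 4.8.4 and the schedule allow it.

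This test differs from the others in the waiver because of what it guards against. The exclusion criteria bar a "Female participant who is pregnant, lactating or planning pregnancy during the course of the study", and Section 4.12 itself says that the vaccine's safety in pregnancy is not known. In Groups 4, 6 and 7, dihydroartemisinin-piperaquine and primaquine also start at that visit. The first exposure would then have a weaker check than the later ones.

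**Working it through.** The protocol states no figure to reproduce. The check is a comparison of texts, with one short piece of arithmetic.

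**1. Is all the text in force?** Yes. Sections 4.8.4 and 4.12 and footnote f are all operative. The amendment history says that version 4.0 introduced the use of recent screening tests for enrolment. The likely cause is that 4.12 was not brought into line then, but the conflict does not depend on that history.

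**2. Where do the rules collide?**

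| Situation | Section 4.8.4 and footnote f | Section 4.12 |
|---|---|---|
| Dose 1, screened 1 to 3 days earlier, urine test repeated on Day 0 | met | met |
| Dose 1, screened 1 to 3 days earlier, urine test carried forward | met | not met |
| Dose 1, screened more than 3 days earlier | no waiver, test required | test required |
| Later doses | no waiver (4.8.5 requires the test) | test required |

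Only the second row is in conflict. The waiver is optional, so a site that tests on Day 0 satisfies every section and can still carry forward microscopy, haematology and biochemistry.

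**3. How much is exposed?**

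- Doses open to the waiver: 1 of 3 per woman in Groups 1 to 6, and 1 of 2 in Group 7.
- Women affected: those of child-bearing age enrolled 1 to 3 days after screening, within an allowed interval of 0 to 30 days (Appendix A, visit intervals).
- Number of such first doses: the protocol gives neither the sex mix nor the distribution of screening intervals, so the count lies anywhere between 0 and the number of women enrolled.

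**4. If a pregnancy were missed, when is the next scheduled test?** Appendix A puts it at Month 1 / Day 0. The interval from dose 1 is 28 days with an allowance of 7 either way: 28 − 7 = 21 days to 28 + 7 = 35 days. This gap is the same for every woman, however dose 1 was cleared. The waiver does not lengthen it. What the waiver changes is the age of the test before dose 1, by at most three days.

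**The case against.** The strongest reply is that the specific text governs. The waiver was adopted on purpose, sits in the section that runs the first-vaccination visit, names the urine pregnancy test and is repeated in the schedule. Section 4.12 offers one general sentence. On that reading a site using the waiver is authorised in two places, and what remains is a sentence left un-updated, which a short exception in 4.12 would cure.

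That carries weight, but it does not settle the matter. Section 4.12 is the protocol's dedicated pregnancy section, it applies its rule to each vaccination, and the text shown gives no order of precedence between sections. An exception in 4.12 would remove the contradiction but keep the weaker check at the first exposure.

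Other points on that side stand and limit the weight of the finding:

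- A negative test within three days is still required, eligibility is checked again and new symptoms are assessed before enrolment, women planning pregnancy are excluded, and contraception is requested during the vaccination period.
- Section 4.5, which makes pregnancy an absolute contraindication, concerns further doses. For dose 1 the exclusion criterion is the rule that matters.
- The 21 to 35 days to the next test is not caused by the waiver.
- Any change has to go to the ethics committees and regulatory authorities under Section 11.3.

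**Conclusion.** The concern holds. Section 4.12 and the carry-forward rule cannot both be met at dose 1 when the screening pregnancy test is used one to three days later, and the deviation status of that practice is left unclear. The expected number of pregnancies missed because of it is very small and cannot be quantified from the protocol. Nothing in the immunogenicity or safety analyses, the power or the sample size changes. It is still worth correcting: it concerns a safety check before the first exposure to the vaccine and, in three groups, to the antimalarials, and the correction is cheap. The conclusion assumes only that the sections rank equally, since the protocol text at hand states no precedence.

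**What to change.** Delete the urine pregnancy test from the carry-forward list in Section 4.8.4, where it appears twice, and from Appendix A footnote f. Keep the three-day waiver for parasite microscopy, haematology and biochemistry. Section 4.12 then stands as written, and dose 1 follows the same rule as the later doses.

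The cost is three wording deletions, submitted as an amendment for approval, and one urine test with an immediate result at a visit where Appendix A already schedules it. If the sponsor prefers to keep the waiver for this test, the least it should do is write the exception into 4.12, accepting that the check at first exposure stays weaker.

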4.8.6 Follow up assessments

Follow-up assessments (visits not involving vaccination) will be done according to the schedule of procedures (Appendix A). Information will be recorded in the CRF for follow-up visits. All participants will be reviewed according to the schedule, either by attending the clinic or being visited at home by a health visitor.

Diary cards will be reviewed for details of solicited and unsolicited AEs, and any new or undocumented medical issues or symptoms that have arisen will also be assessed and recorded in the adverse event CRF. Further clinical assessment in the form of detailed history and physical examination will be undertaken if appropriate.

4.8.7 Blood tests

Blood will be drawn at the time points indicated in the schedule of procedures (Appendix A) and the following laboratory assays performed:

At screening:

- Haematology: haemoglobin [Hb], leukocytes [white blood cells; WBC] and platelets [PLT].
- Biochemistry: alanine aminotransferase [ALT], aspartate aminotransferase [AST] and creatinine [CREA].

- Diagnostic serology: HBsAg, HCV antibodies, HIV antibodies (Counselling will be given prior to testing blood for these blood-borne viruses)
- Parasite microscopy*

At M0, D0: Parasite microscopy*, Haematology: Hb, WBC, PLT, Biochemistry: ALT, AST, CREA, anti-CS antibody; Pharmacokinetics** (piperazine and primaquine drug levels will be assessed if additional data are required)

At M0, D1: Pharmacokinetics** (piperazine and primaquine drug levels)

At M0, D2: Pharmacokinetics** (piperazine drug levels)

At M0, D7: Haematology: Hb, WBC, PLT; Biochemistry: ALT, AST, CREA; Pharmacokinetics** (piperazine drug levels)

At M1, D0: Parasite microscopy*, anti-CS antibody; Pharmacokinetics** (piperazine drug levels)

At M1, D1: Pharmacokinetics** (piperazine and primaquine drug levels)

At M1, D2: Pharmacokinetics** (piperazine drug levels)

At M1, D7: Haematology: Hb, WBC, PLT; Biochemistry: ALT, AST, CREA; Pharmacokinetics** (piperazine drug levels)

At M2, D0: Parasite microscopy*, anti-CS antibody; Pharmacokinetics** (piperazine drug levels)

At M2, D1: Pharmacokinetics** (piperazine and primaquine drug levels)

At M2, D2: Pharmacokinetics** (piperazine drug levels)

At M2, D7: Haematology: Hb, WBC, PLT; Biochemistry: ALT, AST, CREA; Pharmacokinetics** (piperazine drug levels)

At M3: Parasite microscopy*, Haematology: Hb, WBC, PLT; Biochemistry: ALT, AST, CREA; anti-CS antibody

At M6: Parasite microscopy*, anti-CS antibody

* In the unexpected event that volunteers are found to be parasitaemic during screening, baseline or during vaccination or follow-up visits they will be treated according to the most up-to-date government guidelines. If at screening or baseline, these volunteers will be excluded from participation in the study. If at Month 1 or Month 2 vaccination days, these volunteers will be withdrawn from further study vaccination.

** Samples for pharmacokinetics will only be taken for subjects in Groups 4 and 6. Additional drug level assessment for Primaquine will be done if additional data are required

Samples collected for screening assays including haematology, biochemistry, diagnostic serology and parasite microscopy will be tested at Bangkok Hospital for Tropical Disease Laboratory, Faculty of Tropical Medicine, Mahidol University.

Samples collected for drug levels assessment (piperazine and primaquine) will be tested at the Department of Clinical Pharmacology Laboratories, Faculty of Tropical Medicine, Mahidol University.

Samples collected for assessment of antibody responses will be processed at the site and serum samples will be stored at -20C or below until shipment to a biorepository sample management laboratory (Precision) and will then be shipped to the Walter Reed Army Institute of Research (WRAIR) for testing. The following assays will be conducted at the WRAIR laboratories in Silver Spring, United States:

Component	Method	Kit / Manufacturer	Unit	Cut-off	Laboratory
Plasmodium falciparum . Circumsporozoite Protein.(NANP)6 Ab.IgG	ELISA	In house	EPT or ug/ml	100	WRAIR
Plasmodium falciparum . Circumsporozoite Protein.(NANP)6 Ab.IgG Avidity	ELISA	In house	Avidity index	Not applicable	WRAIR
Plasmodium falciparum . anti-C-Term Circumsporozoite Ab.IgG	ELISA	In house	EPT	100	WRAIR
Plasmodium falciparum . anti-C-Term Circumsporozoite Ab.IgG avidity	ELISA	In house	Avidity Index	Not applicable	WRAIR
Plasmodium falciparum . Circumsporozoite Full length (N+C-Terminal)	ELISA	In house	EPT	100	WRAIR
P falciparum . anti-full length CSP Ab.IgG avidity	ELISA	In house	Avidity Index	Not applicable	WRAIR

ELISA: Enzyme-linked immunosorbent assay; EPT: endpoint titer; IgG: Immunoglobulin G; WRAIR: Walter Reed Army Institute of Research

These assays allow the characterisation of B cell responses elicited by RTS,S/AS01, quantification of anti-CSP titers and avidity index (NANP repeat region, C-terminus, and full length). This will enable bridging back to earlier trials with RTS,S/AS01.

With the volunteers' informed consent, any leftover serum will be frozen for up to 5 years for future immunological analysis of malaria-specific responses. This may include human DNA and RNA analysis to search for correlates of vaccine immunogenicity and efficacy.

